2. SYNOPSIS

Trial Title	Oxford Acute Myocardial Infarction - Pressure-controlled Intermittent Coronary Sinus Occlusion in STEMI
Internal ref. no. (or short title)	OxAMI-PICSO
Clinical Phase	II
Trial Design	Prospective single centre observational cohort study

Trial Participants	Patients admitted for primary percutaneous coronary intervention for ST elevation myocardial infarction	
Planned Sample Size	75 patients	
Treatment duration	Maximum of 90 minutes	
Follow up duration	6 months	
Planned Trial Period	18 months	
	Objectives	Outcome Measures/Endpoints
Primary	To evaluate the effect of pressure intermittent controlled coronary sinus occlusion on the indexes of coronary physiology and on infarct size in STEMI patients at short and mid term follow up.	To evaluate the effect of pressure intermittent controlled coronary sinus occlusion on infarct size measured at cardiac magnetic resonance after 24-48 hours from revascularization.
Secondary	To evaluate the utility of individual biomarkers (blood components derived substances from cells, DNA, plasma etc) in the assessment of coronary artery disease and myocardial infarction investigating also how these individual biomarkers may be modified by PICS0 treatment.	To evaluate the effect of pressure intermittent controlled coronary sinus occlusion on humoral biomarkers and on the evolution of parameters of coronary physiology at 24 hours and infarct size, microvascular obstruction at cardiac magnetic resonance after 6 months from revascularization.
Safety Endpoint	To evaluate the rate of PICS0 failure deployment, coronary sinus complications, and additional time and radiation exposure associated to for PICS0 deployment	
Device name	Pressure intermittent controlled coronary sinus occlusion (PICS0)	
Device Manufacturer	Miracor Medical System	
Device Classification	Interventional Cardiology	

Protocol version no.	Effective Date	Significant Changes	Previous protocol version no.
2.0	01.04.2015	- Clarification of follow up duration - Clarification for what group of patient CMR follow up is meant	v1.0 13.02.2015
3.0	20.06.2016	- Extension of sample size to 75 patients to achieve a minimum of 25 patients with complete dataset	v2.0 01.04.2015

Protocol version no.	Effective Date	Significant Changes	Previous protocol version no.

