4.0	06.05.2016	
 - Change in information about regulatory status of PICSO technology from CE-marked to non non-CE mark - Extension of recruitment beyond the period specified in the IRAS application form 	V3.0 20.06.2016
5.0	26.02.2018	
 - Extension of recruitment beyond the period specified in the IRAS application form - Extension of inclusion criteria to allow enrolment of all patients with ST elevation myocardial infarction, irrespectively of the coronary location of the culprit lesion 	V4.0 06.05.2016

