5. OBJECTIVES AND OUTCOME MEASURES/ENDPOINTS

Objectives	Outcome Measures/Endpoints
------------	----------------------------

Primary Objective
 
To assess the impact of PICSO on coronary physiology parameters, on infarct size, on myocardial salvage and on microvascular obstruction at CMR in a selected population of STEMI patients at higher risk of no reflow and with the theoretical prerequisites that make more likely to respond to PICSO treatment. The control group will be represented by a highly matched group of patients from the ongoing Ox-AMI (Oxford Acute Myocardial Infarction) project (Ethics Ref 11/SC/0397), who have undergone all other aspects of the study protocol, including assessment of coronary physiology at 24 hours post primary PCI, 24-48 hours and 6 months CMR, but who have not received PICSO treatment.
	
Area at risk, Infarct size, Myocardial salvage and microvascular obstruction measured by cardiac magnetic resonance at 24-48 hours

Secondary Objectives
 
The OxAMI-PICSO study aims to evaluate the utility of individual biomarkers (blood components derived substances from cells, DNA, plasma etc) in the assessment of coronary artery disease and myocardial infarction. The OxAMI-PICSO may show also how these individual biomarkers may be modified by PICSO treatment.
	
Coronary flow reserve (CFR), Fractional Flow reserve (FFR), index of microcirculatory resistance (IMR) measured at 24 hours after PCI.
 
Infarct size and microvascular obstruction extent measured by cardiac magnetic resonance at 6 months
 
Individual Biomarkers related to coronary artery disease/myocardial infarction at three time points (PCI, 24/48 hours after PCI and 6 months). These include: blood biomarkers of myocardial injury, metabolism and inflammation.

Tertiary Objectives
 
To evaluate the rate of PICSO failure deployment, coronary sinus complications, and additional time and radiation exposure associated to for PICSO deployment
	
Rate of PICSO failure deployment
 
Rate of coronary sinus complications: perforation, dissection, thrombosis
 
Time for PICSO deployment / additional screening time and radiation dose

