8.3.1 Stage 1: Pre-Stenting

- Diagnostic angiography will be performed in the standard manner using appropriate catheters.
- Bivalirudin will be administered (0.75mg/kg bolus followed by an infusion of 1.75 mg/kg/min for up 4 hours after the procedure as clinically warranted), as routinely used for PCI. The lesion will be

crossed with a coronary guide wire in the usual manner for PCI. Normal blood flow will be rapidly achieved by thrombus aspiration and/or predilation

3. Pre-stenting coronary physiology parameters, namely FFR, CFR and IMR, will be measured, using a pressure wire, as used for routine clinical measurements in patients undergoing PCI.
4. If pre-stenting IMR is > 40 , patients will be invited to receive the PICSO device. If pre-stenting IMR is ≤ 40 PICSO device will not be proposed, but the patient will be invited to remain in the study for serial blood sampling (procedural-6 hours-24 hours and 48 hours) and routine clinical data collection.

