The PICSO Impulse Catheter is then connected to the PICSO Impulse console. The PICSO Impulse Console automatically operates the PICSO Impulse Catheter. The balloon is intermittently inflated and deflated using helium, based on coronary sinus pressure and synchronized with the ECG. The monitor displays the inflation/ deflation state of the balloon, as well as trend graphs and time counters; Live graphs display curves and numeric values of ECG, coronary sinus pressure, aortic pressure and auxiliary input. It is easy to use and provides direct feedback on the patient's individual therapy using the 'PICSO Dose', which is defined as the sum of the coronary sinus pressure modulation for all PICSO cycles applied. All data are automatically stored and can be retrieved for later analysis for each patient. The unit is transportable and runs on battery supply if needed during patient transportation.

Once the PICSO Impulse catheter is connected to the consoled, by activating the "START" button, the distal balloon will be cyclically inflated. Each cycle starts with a balloon inflation triggered by QRS

complex on ECG monitoring. During balloon inflation coronary sinus pressure will progressively increase till reaching a plateau, then coronary sinus occlusion is stopped by balloon deflation. For security, each balloon inflation has a maximum limit of 30 seconds in duration. The deflation interval between two cycles has a minimum duration of 3 seconds.

In the OxAMI-PICSO the PICSO Impulse system will be adopted in a highly selected population of patients with ST elevation myocardial infarction, characterized by a possibly impaired microvasculature impairment at the time of the PCI, as expressed by a prestenosing elevated index of microcirculatory resistance (> 40). The aim is to assess the extent of infarct size after 24-48 hours in such specific group of patients. Propensity-score matched historical patients from the ongoing OxAMI study will be controls in the OxAMI-PICSO study.

All the investigators using the PICSO device will undergo a specialist training programme completion, including the performance of the first cases under the supervision of a proctor expert. Educational training sessions for use of the PICSO will be provided to all clinical staff (nurses, radiographers, physiologists) involved in the care of patients who have received PICSO.

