12.2 Analysis of Endpoints

In keeping with our usual practice we will obtain expert statistical advice from the Centre for Statistics in Medicine (or equivalent) for each specific task. Summary statistics, including means, medians, and

variances, will be calculated at each time point and for each type of data (e.g. parameters derived from coronary physiology and CMR). The distribution of the levels will be described. It may be necessary to log transform the data before further statistical analysis. For each parameter an analysis of variance will be carried out at each time point.

Control group in OxAMI-PICSO study is represented by a highly matched group of patients underwent to primary PCI, with a prestenosing IMR > 40 and with available 24 hours recath and 24-48 hours/6 months CMR data. Matching will be performed by application of a propensity score matching analysis including the following predictors in the model: age, sex, pain to wire time, thrombotic burden (assessed as angiographic thrombus score), thrombus aspiration performance, stent volume, glycoprotein IIbIIIa inhibitors adoption.

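### Area at risk is listed as a primary outcome and tested like infarct size, although the order of the procedure makes it mainly a measure of balance between PICSO patients and historical controls

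*Combined protocol and SAP*

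**What the plan says.** All references are to the combined protocol and SAP.

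- **Section 5, primary outcome cell:** "Area at risk, Infarct size, Myocardial salvage and microvascular obstruction measured by cardiac magnetic resonance at 24-48 hours". Area at risk comes first of four measures.
- **Section 5, primary objective:** apart from coronary physiology, the objective is the impact of PICSO "on infarct size, on myocardial salvage and on microvascular obstruction at CMR". Area at risk is not named.
- **Synopsis, primary endpoint:** "infarct size measured at cardiac magnetic resonance after 24-48 hours from revascularization", and nothing else.
- **Section 12.2, analysis:** "For each parameter an analysis of variance will be carried out at each time point". No covariate is named, and area at risk is given no separate role.
- **Section 8.3.1, Stage 1:** "Normal blood flow will be rapidly achieved by thrombus aspiration and/or predilation". Pre-stenting IMR is then measured, and PICSO is deployed in Stage 2 (Section 8.3.2).
- **Section 10.1, controls:** "Propensity-score matched historical patients from the ongoing OxAMI study will be controls in the OxAMI-PICSO study".
- **Section 12.2, matching variables:** "age, sex, pain to wire time, thrombotic burden (assessed as angiographic thrombus score), thrombus aspiration performance, stent volume, glycoprotein IIbIIIa inhibitors adoption". Culprit vessel, infarct location and area at risk are absent.
- **Version 5.0 entry in the amendment history:** the inclusion criteria now allow "enrolment of all patients with ST elevation myocardial infarction, irrespectively of the coronary location of the culprit lesion". Current Section 7.2 agrees, with no restriction on location.

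**The concern.** Area at risk is the myocardium supplied by the occluded artery. In this study the occlusion is relieved before the device is in place, so PICSO cannot change which territory was occluded. With non-randomised controls, a group difference in area at risk is therefore mainly a sign that the groups contain different patients. Listing it as a primary outcome and giving it the same test as infarct size leaves it unclear how such a difference is to be read.

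The larger consequence is for infarct size. A bigger territory tends to produce a bigger infarct, so an imbalance carries over into the infarct-size comparison. A smaller area at risk in the PICSO group would inflate the apparent effect, and a larger one would hide a real effect. The plan collects the measure that would reveal this but does not say it will be used that way.

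**Working it through.** **1. Which sections make area at risk primary**

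| Place | Area at risk included? |
|---|---|
| Synopsis, primary endpoint | No, infarct size only |
| Section 4.3, hypothesis | No |
| Section 5, primary objective text | No |
| Section 5, primary outcome cell | Yes, listed first |
| Section 10.1, stated aim | No, infarct size only |
| Section 12.1, sample size | No, infarct size only |

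Its primary status rests on one table cell, which conflicts with the synopsis.

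**2. Why imbalance is plausible**

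Controls are historical and matched on seven variables. None of these identifies the territory supplied by the culprit artery. Current eligibility admits any culprit location, so territory can differ systematically between groups. The documents do not say by how much.

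**3. Inputs for the size of the effect**

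From Section 12.1: 25 per arm and a planned 29% reduction in infarct size. No mean or SD is given for infarct size or area at risk, so everything below that uses a coefficient of variation (CV) or a correlation is an assumption.

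The one indirect handle is the initial figure of 12 per group. Sidedness is not stated; taking two-sided 5% and 80% power, n = 2(1.96 + 0.84)² × CV² / 0.29². A CV of 0.25 gives 11.7, rounded up to 12, and the figure 12 results for CVs of 0.243-0.253. This does not confirm that value, so a range of 0.25-0.50 is used.

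**4. Shift in infarct size from a systematic imbalance**

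Relative shift = r × (CV of infarct size / CV of area at risk) × imbalance. With equal CVs and a 10% imbalance:

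- r = 0.5: 0.5 × 1 × 10% = 5%
- r = 0.8: 0.8 × 1 × 10% = 8%
- strict proportionality: 10%

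Applied to a true 29% reduction, with the shift taken as multiplicative:

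| Shift in infarct size | Observed if area at risk is smaller with PICSO | Observed if it is larger with PICSO |
|---|---|---|
| 5% | 1 − 0.71 × 0.95 = 32.6% | 1 − 0.71 × 1.05 = 25.5% |
| 8% | 1 − 0.71 × 0.92 = 34.7% | 1 − 0.71 × 1.08 = 23.3% |
| 10% | 1 − 0.71 × 0.90 = 36.1% | 1 − 0.71 × 1.10 = 21.9% |

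**5. False favourable results with no true effect**

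Two-sided 5% t-test, 25 per arm, 48 degrees of freedom, noncentrality = shift / (CV × √(2/25)). With no imbalance the favourable tail is 2.5%.

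| Shift in infarct size | CV 0.25 | CV 0.40 | CV 0.50 |
|---|---|---|---|
| 5% | 10.3% | 6.3% | 5.3% |
| 8% | 19.7% | 10.3% | 8.0% |
| 10% | 28.3% | 13.7% | 10.3% |

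These rates follow from an imposed imbalance; they do not estimate what this study will show. An imbalance in the other direction would lower the favourable tail and cost power.

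**6. What adjustment gains**

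Adjusting infarct size for area at risk multiplies its standard error by about √(1 − r²):

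- r = 0.5: √0.75 = 0.866, a 13% cut, worth 25/0.75 ≈ 33 per arm unadjusted
- r = 0.8: √0.36 = 0.600, a 40% cut, worth 25/0.36 ≈ 69 per arm unadjusted

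The formula ignores the small cost of one extra parameter and of any group difference in the covariate.

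In simulation (no true effect, infarct size proportional to area at risk, 10-20% imbalance, CV of area at risk 0.30 or 0.40), adjusted infarct size kept the favourable error at 2.5-3.0%. Unadjusted infarct size gave 10-13% at 10% imbalance and 33-44% at 20%. The adjusted model matches how those data were generated, so this shows the best case for adjustment.

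**The case against.** **No success rule.** A reader might infer that a smaller area at risk would be claimed as a benefit. The documents do not support that. No section gives area at risk a direction, hypothesis or success criterion, and Section 12.2 says expert statistical advice will be sought for each task. What stands is that its role is undefined.

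**Infarct size is the real primary endpoint.** The synopsis, the stated aim and the sample size all point that way. This is a fair reading, but it makes the Section 5 cell something to correct. It also leaves the infarct-size comparison unadjusted.

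**Salvage already uses area at risk.** It is a listed outcome, and area at risk may appear beside it only as a component. But salvage is not defined. If it means area at risk minus infarct size, a smaller area at risk would lower salvage while infarct size looked better, and the plan gives no rule for reading such a mixed result.

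**Chance differences do no harm.** This is correct. Chance variation in area at risk is already inside the standard error of unadjusted infarct size and does not raise type I error. Comparing the spread expected by chance with the planned 29% effect would therefore mislead. The bias argument needs systematic imbalance, for which the documents give a plausible route but no size.

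**Area at risk is imaged after treatment.** This is the strongest objection to adjustment. Section 4 names tissue oedema among the mechanisms of no reflow, Section 4.2 attributes washout of inflammatory factors to PICSO, and Section 9.3 gives no CMR method for area at risk. If PICSO alters the measured value, adjustment could remove part of a real effect and the balance reading would be less clean. The adjusted analysis should therefore be supportive only.

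**Conclusion.** The point holds as a gap in definition and analysis. It does not show that the primary comparison is invalid. Area at risk is primary only in the Section 5 outcome cell, against the synopsis and the objective text. By the protocol's own sequence it mainly reflects who is in each group, and the unadjusted analysis leaves infarct size exposed to imbalance in either direction.

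Under the assumed correlation of 0.5-0.8 and equal CVs, a systematic 10% imbalance moves infarct size by about 5-8%, and by at most 10% under strict proportionality. Adjustment would cut the standard error by 13-40%. The existence and size of any imbalance are not known from the documents. The change is worth making because it is cheap and uses data already planned.

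**What to change.** 1. **Synopsis and Section 5:** reconcile the two statements of the primary outcome. Move area at risk out of the outcome cell and describe it as a reference and balance measure.
2. **Section 12.2, reporting:** report area at risk by group with its standardised difference, and state that a group difference will not be read as an effect of PICSO.
3. **Section 12.2, analysis:** add a prespecified supportive analysis of 24-48 hour infarct size adjusted for area at risk, reported beside the unadjusted result.
4. **Additional adjustment:** because area at risk is imaged after treatment, use a pre-treatment marker of territory, such as culprit vessel, as a further adjustment. State the CMR method for area at risk and the definition of salvage.

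**Cost:** a few lines of text and one or two extra models. Area at risk is already planned, and culprit vessel should be available from the angiogram. The downside is possible over-adjustment if PICSO changes measured area at risk, which is why the unadjusted result stays in the report.

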8.3.3 Stage 3: Stenting

1. Stenting is performed as usual clinical practice.
2. Post-dilation is left to operator's discretion, as in clinical routine.
3. At the end of the procedure a final reassessment of coronary physiology parameters is performed again as previously described.

Blood samples may be taken, (by 5 or 10 ml syringes), at the following time-points, from both peripheral vein (V), using the venous cannula, from the coronary sinus (CS) using a CS sampling catheter, or the PICSO delivery sheath, and from the coronary artery (C) either via the guide catheter used for the procedure or an aspiration catheter placed through the guide catheter:

Sampling point (1): beginning of procedure	V, C
Sampling point (2): placement of PICSO device	V, CS, C
Sampling point (3): end of procedure	V, CS, C
Sampling point (4): end of PICSO treatment period	V, CS,
Sampling point (5): 6 hours after 1 st stent deployment	V

For patients in whom an aspiration catheter or protection device is used during PCI, blood, thrombus and/or atheromatous plaque material may be retrieved during the procedure. These materials, which are usually discarded, will be retained for analysis. Data on the PCI procedure and any device or technology used will be collected.

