10. IDENTIFICATION & DESCRIPTION OF THE INVESTIGATIONAL DEVICE

10.1 Device description

The PICSO Impulse System consists of the PICSO Impulse console (101.100.000.000) and PICSO impulse catheter (300.100.000.010) by Miracor Medical Systems ([name]).

PICSO Impulse Console

PICSO Impulse Catheter

Each PICSO Impulse catheter will have a serial number, which will be recorded for traceability during and after completion of the study.

The PICSO Impulse catheter presents a balloon at the distal end. The balloon inflates and deflates cyclically once deployed in the coronary sinus, leading to intermittent coronary sinus pressure increase. This intermittent increase in coronary sinus pressure leads to an improved perfusion of the ischemic

area with potential benefit in terms of myocardial salvage through 3 mechanisms: 1) redistribution of blood flow from the remote myocardium to the border zone of the ischemic myocardium [14]; 2) enhanced wash out of noxious, inflammatory factors and embolic material across the microvascular bed (suction effect upon balloon release) [15]; 3) improvement in collaterals through release of vascular growth factors as consequence of venous pressure increase [16-17].

The PICSO Impulse catheter is a 8F double lumen catheter with a 15.5x20mm long balloon at the distal end. The catheter is connected to the console through two pneumatic tubes in which helium is shuttled to and from the balloon. In addition, the coronary sinus pressure is monitored through the center lumen of the catheter. The catheter is placed in the coronary sinus over a 0.025' wire by a 8.5Fr pre-shaped delivery long steerable sheath (Oscor Destino Steerable Sheath DS856750/22) inserted in the femoral vein. Femoral vein access is obtained as routine practice according to Seldinger technique. Once the catheter is placed, the guidewire is removed and the steerable sheath is retracted in the right atrium for support. PICSO deployment median time has been estimated to be of 12 minutes (Interquartile Range 9-18 minutes)

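### The biomarker endpoint treats 'PCI' as one time point although four samples span it, and the planned ANOVA leaves the pre-PICSO sample unused as a baseline

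*Combined protocol and SAP*

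**What the plan says.** Section 5 gives the biomarker endpoint as "Individual Biomarkers related to coronary artery disease/myocardial infarction at three time points (PCI, 24/48 hours after PCI and 6 months". It names no sample, vessel or baseline for the PCI time point.

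Section 8.3.3 lists the samples around the procedure:
- "Sampling point (1): beginning of procedure": peripheral vein and coronary artery
- "Sampling point (2): placement of PICSO device": vein, coronary sinus and coronary artery
- "Sampling point (3): end of procedure": the same three sites
- "Sampling point (4): end of PICSO treatment period": vein and coronary sinus

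A fifth sample, venous only, follows 6 hours after the first stent. Appendix A has the same sequence and then separate 24-hour, 48-hour and 6-month columns. For patients with IMR of 40 or less, Section 8.3.1 describes "serial blood sampling (procedural-6 hours-24 hours and 48 hours". Appendix B shows their in-procedure samples as start and end of PCI only.

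Section 12.2 states: "For each parameter an analysis of variance will be carried out at each time point". It allows a log transformation but names no baseline covariate. Sections 4.3 and 12.2 make the controls earlier OxAMI patients with pre-stenting IMR above 40, matched by propensity score. The score uses two demographic variables, ischaemic time, thrombus score, stent volume and two treatment variables. It contains no biomarker.

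**The concern.** The secondary objective includes how PICSO modifies biomarkers. That requires a value from before the device acts, a value from after, and a comparison that keeps them apart. The trial collects the first but gives it no role. A single label covers samples from before the device starts until it stops, so the sample and vessel behind a reported PCI result could be settled after the data are seen. The 6-hour sample is the first one scheduled after the procedure and device period, and it has no place in the endpoint as listed.

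The groups are not randomised. A comparison that ignores the starting level cannot separate a PICSO effect from a difference that was already present.

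**Working it through.** The documents state no sample size, SD or power for biomarkers, so there is no planned figure to reproduce.

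**Step 1. Set the schedule beside the endpoint.** (V = peripheral vein, C = coronary artery, CS = coronary sinus.)

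| Sample | Site | Relation to PICSO | Section 5 time point |
|---|---|---|---|
| Beginning of procedure | V, C | before | PCI |
| PICSO placement | V, CS, C | at start | PCI |
| End of procedure | V, CS, C | after start | PCI |
| End of PICSO | V, CS | at stop | PCI, presumably |
| 6 h | V | after | none |
| 24 h and 48 h | V | after | merged |
| 6 months | blood | after | 6 months |

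Placement and end-of-PICSO samples are defined by the device, so no control can have them. The coronary sinus is not sampled at the beginning, and the coronary artery is not sampled after the procedure. Only peripheral venous blood can serve as a baseline for the later points.

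**Step 2. What the unadjusted comparison estimates.** Let τ be the PICSO effect, d the pre-treatment difference in mean log marker between groups, b the within-group slope of the later value on the start value, and ρ their correlation.
- ANOVA estimates τ + b·d.
- Analysis of covariance subtracts b·d and multiplies the residual variance by about (1 − ρ²).

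Write δ = b·d in outcome SDs. With 25 per arm, two-sided 5% and τ = 0, the rejection rate is Φ(δ/√(2/25) − 1.96) + Φ(−δ/√(2/25) − 1.96), where √(2/25) = 0.283.
- δ = 0: 5%.
- δ = 0.25 (assumed): 0.25/0.283 = 0.88, giving 14.3%.
- δ = 0.5 (assumed): 0.5/0.283 = 1.77, giving 42.4%.

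The documents give neither d, b nor ρ, so these rates show sensitivity and are not estimates.

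**Step 3. Possible readings of PCI.**
- *Each sample analysed separately:* nothing is mixed. Step 2 still applies, and two of the four samples have no control counterpart.
- *Start sample only:* no timing offset, but the sample precedes PICSO and cannot show its effect.
- *Average of the samples:* an effect present only at the last two venous samples is diluted to 2/4. For coronary samples 1/3 remains.
- *End-of-procedure or last sample:* treated patients may be sampled later. Section 10.1 says "PICSO deployment median time has been estimated to be of 12 minutes (Interquartile Range 9-18 minutes", and Section 16.2 allows around 20 extra minutes on a procedure of about 60, a figure that includes physiology measurements.

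**Step 4. Timing, for illustration only.** The matched controls' in-procedure sampling times are not given, so the Appendix B pattern (0 and 60 min) stands in for them. Assumed PICSO-group times are 0, t, 80, and t + 60 or t + 90 min, with t = 15 or 30. The 80 adds the full 20 minutes, which is an upper bound. The 60 to 90 min duration is from Section 8.3.2.
- Start sample: offset 0 min.
- End of procedure: 80 − 60 = 20 min.
- Mean of all: from (0+15+80+75)/4 − 30 = 12.5 to (0+30+80+120)/4 − 30 = 27.5 min.
- Last sample: 80 − 60 = 20 to 120 − 60 = 60 min.

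For a marker rising by an assumed 0.5 SD per hour, with no PICSO effect, the Step 2 formula gives 5%, 9.1%, 6.6–12.8% and 9.1–42.4% respectively. A marker that is stable during the procedure gives 5% under every rule.

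**The case against.** A reader might infer that the plan builds one PCI value mixing baseline with outcome, so that the groups must differ even if PICSO does nothing. The documents do not support that. No section averages, pools or selects among the PCI samples. Section 8.3.3 itself presents its sampling points as time points, and Section 12.2 analyses each time point, so point-by-point analysis is the natural reading. It would also give the 6-hour sample an analysis.

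The timing illustration leans on Appendix B, which covers concurrent patients without the device and not the matched OxAMI controls. A false difference also needs a marker that changes during the procedure and a rule that uses later or pooled samples. All of this stands.

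It can also be said that covariance analysis is a preference, that Section 12.2 provides for expert statistical advice, and that matching on ischaemic time already narrows pre-treatment differences in injury markers. The last point is fair but partial, because no biomarker is in the score. In a randomised trial the choice would mainly concern precision. With historical matched controls it also concerns bias. A promise of advice does not specify a baseline.

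**Conclusion.** The point holds as two linked gaps. First, the PCI time point is undefined: four samples, up to three vessels and no rule, with the 6-hour sample left outside the endpoint. Second, under every reading, the unadjusted ANOVA leaves pre-treatment biomarker differences between non-randomised groups in the estimated effect and forgoes a variance reduction of about ρ².

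The size of the bias cannot be computed from the documents. The rates above rest on 25 per arm and on assumed offsets, and those for timing also rest on a substitute control schedule. Mixing of pre- and post-PICSO values is a possibility to be closed off, not an established fault. Only a secondary endpoint is affected.

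**What to change.** **Section 5.** Define the beginning-of-procedure peripheral venous sample as baseline. List end of procedure, 6 h, 24 h, 48 h and 6 months as separate outcome points. Label the PICSO-placement and end-of-PICSO samples as descriptive within the PICSO group.

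**Section 12.2.** For each biomarker and outcome point, replace the plain ANOVA with analysis of covariance, on the log scale where needed, adjusted for the patient's own baseline value. Report sampling times by group, and interpret the end-of-procedure comparison with caution because PICSO placement lengthens the procedure.

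Two tempting additions should be left out. A missing-baseline indicator can itself bias a non-randomised comparison. Adjustment for clock time should not be relied on, because sampling time is partly a consequence of device placement and is entangled with group. Report instead how many patients in each group lack a start sample.

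**Cost.** Wording and slightly more analysis, with no new sampling points or patients. Start-of-procedure values and sampling times must be available from OxAMI records for controls, which the documents do not confirm. Section 8.3.3 words sampling as optional, so the baseline sample should be marked as required. Adjustment for one measured baseline will not remove other differences between treated patients and historical controls.
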